4.2 OTHER TREATMENTS, EMERGENCY PROCEDURES, RESTRICTIONS

4.2.1 Other treatments and emergency procedures

Concerning the 6MWT, the following is required:

The test should be performed in a location where a rapid, appropriate response to an emergency is possible. Adequate safety equipment must be readily available at the test site according to local institutional requirements and emergency medications are to be administered at the discretion of the Investigator such as: oxygen, fast-acting nitrate, antiplatelet agent, sphyngomanometer and telephone.

The 6MWT should be immediately stopped in case of acute chest pain, sudden pallor, loss of coordination / staggering, mental confusion, extreme dyspnea, leg cramps, diaphoresis. The subject should be monitored in the unit until the signs / symptoms / ECG modifications have been completely cleared.

The use of medication for the treatment of HF will be in accordance with local/international guidelines and at the discretion of the Investigator.

All concomitant (additional) medications and other therapies should be recorded on the appropriate pages of the eCRF.

Concomitant antidiabetic medications should be adjusted individually as clinically indicated by the patient's usual diabetes care provider. Restrictions of antidiabetic background therapy are described in [section 4.2.2](#).

Patients without a diagnosis of DM experiencing repeated or severe symptoms such as nervousness, sweating, intense hunger, trembling, weakness and palpitations should contact the Investigator or other healthcare professional, as these symptoms might be suggestive of hypoglycaemia. In the case of hypoglycaemia, in patients with or without DM, that may put the patient at risk (e.g. repeated symptomatic hypoglycaemia or severe hypoglycaemia), appropriate care should be provided at the discretion of the Investigator.

Special attention must be paid to the prevention of ketoacidosis. All patients must be made aware of this risk and need to be instructed to contact the Investigator or other healthcare professional in case of symptoms of metabolic acidosis, ketoacidosis and DKA.

Cases of DKA have been reported in T2DM patients treated with empagliflozin, including fatal cases. In a number of reported cases, the presentation of the condition was atypical with only moderately increased blood glucose values; below 14 mmol/l (250 mg/dl).

The risk of DKA must be considered in the event of non-specific symptoms such as nausea, vomiting, anorexia, abdominal pain, excessive thirst, difficulty breathing, confusion, unusual fatigue or sleepiness.

Patients should be assessed and treated for ketoacidosis immediately according to local guidelines if these symptoms occur, regardless of blood glucose level. If ketoacidosis is suspected, the trial medication should be discontinued, the patient should be evaluated, and prompt treatment should be initiated.

Patients who may be at higher risk of ketoacidosis while taking empagliflozin include patients on a very low carbohydrate diet (as the combination may further increase ketone body production), patients with an acute illness, pancreatic disorders suggesting insulin deficiency (e.g., history of pancreatitis or pancreatic surgery), insulin dose reduction (including insulin pump failure), alcohol abuse, severe dehydration, and patients with a history of ketoacidosis. Empagliflozin should be used with caution in these patients. In patients requiring insulin, caution should be taken when the dose of insulin is reduced.

In clinical situations known to predispose to ketoacidosis (e.g. prolonged fasting due to acute illness or surgery), the Investigator should consider monitoring for ketoacidosis and temporarily discontinue the trial medication.

In patients with heart failure who receive empagliflozin, elderly patients with heart failure and in case of conditions that may lead to fluid loss (e.g. gastrointestinal illness), careful monitoring of volume status (e.g. physical examination, laboratory tests including haematocrit), blood pressure measurement and electrolytes is recommended since empagliflozin may potentially lead to hypotension. Temporary interruption of the study drug should be considered until the fluid loss is corrected.

Temporary interruption of empagliflozin should be considered in patients with complicated urinary tract infections.

4.2.2 Restrictions

4.2.2.1 Restrictions regarding concomitant treatment

The use of any SGLT-2 inhibitors or combined SGLT-1 and 2 inhibitors, except the blinded trial medication, is prohibited during the course of the trial. This also includes the 7 day period between the End of Trial (EOT) and the Follow Up Visit.

Consistent with prevailing CV guidelines, if oral diuretics are prescribed, patients must be on an appropriate and stable dose for 2 weeks prior to Visit 1 to control volume status and symptoms.

Concomitant diseases should be treated according to best standard of care in accordance with local guidelines and recommendations.

Patients should not receive treatment with i.v. iron therapy and EPO during the course of the trial.

If any restricted treatment is given during the conduct of the trial, the trial medication must be discontinued temporarily, or if needed permanently.

If the patient is in need of any additional treatment during this period, this may be given at the discretion of the Investigator. The patient can still remain on trial medication.

4.2.2.2 Restrictions on diet and life style

Prior to each visit during which a 6MWT is performed, patients should be advised not to perform vigorous exercise on the day of testing. Patients should be advised to take only a light meal prior to a 6MWT.

Patients must remain in the building where the exercise testing is performed and must return to the study personnel at least 10 minutes prior to the start of the 6MWT.

For further details on restrictions on diet and life style please refer to [appendix 10.1](#).

4.2.2.3 Restrictions regarding women of childbearing potential

Women of childbearing potential must use the contraception methods described in the patient information. For sites in Portugal please refer to the contraception methods described in [appendix 10.8](#).

4.3 TREATMENT COMPLIANCE

Patients are requested to bring all remaining trial medication including empty package material with them when attending visits.

Based on tablet counts, treatment compliance will be calculated as shown in the formula below. Compliance will be verified by the Clinical Research Associate (CRA) authorised by the sponsor.

$$\text{Treatment compliance (\%)} = \frac{\text{Number of tablets actually taken since last tablet count} \times 100}{\text{Number of tablets which should have been taken in the same period}}$$

Compliance should be between 80% and 120%. If the number of doses taken is not between 80-120%, site staff will explain to the patient the importance of treatment compliance. However, randomised patients will not be discontinued for poor compliance without prior discussion with the monitor or designee.

Patients who are not compliant with their medication should again be carefully interviewed and again re-informed about the purpose and the conduct of the trial.

5. ASSESSMENTS

5.1 ASSESSMENT OF EFFICACY

5.1.1 Six Minute Walk Test

At all sites, patients will perform an exercise capacity assessment using the 6-minute walk test. One 6MWT will be performed at the screening visit, visit 3 and the early discontinuation visit (if applicable). At visits 2 and 4, two 6MWTs will be performed at least 1 hour apart for increasing reliability of the test as well as for decreasing variability. The distances from both tests will be recorded in the eCRF and the largest distance measured will be used for analysis. Testing of the 6MWT at each clinic visit should be preferably performed about the same time of day to minimize intraday variability.

The 6MWTs at Visit 1 and 2 will be performed to assess patient eligibility and as well the screening test will serve as the training test to familiarize patients with the procedure. If the distance walked during any of these 6MWTs is > 350m the patient will be considered a screen failure. If the largest distance walked at Visit 2 is < 100m, the patient will be considered a screen failure. The 6MWT of largest distance performed at Visit 2, will be the baseline result.

Prior to and at the end of the 6MWT, patients will be asked to rate their breathing discomfort and overall fatigue using the Borg Scale.

The 6MWT methodology is described in detail in the ISF and [appendix 10.1](#). Please refer to [section 6.2.2](#) for preferred order of completion of assessments.

5.1.2 Kansas City Cardiomyopathy Questionnaire

KCCQ is a commonly used 23 item self-administered questionnaire designed to evaluate physical limitations, symptoms (frequency, severity, and changes over time), social limitations, self-efficacy, and quality of life in patients with HF (refer to [appendix 10.3.1](#)).

The questionnaire takes less than 15 minutes to complete and will be assessed according to the [Flow Chart](#). Please refer to [section 6.2.2](#) for order of completion of patient reported outcome measures.

The Investigator (or designated site-personnel) should ensure that the patient has access to a quiet area at the site where he/she can be left alone to record her/his response in the questionnaire. In instances where a patient cannot give or decide upon a response, no response should be recorded. The Investigator (or designated site-personnel) should check that all items have been completed by the patient, but the response to each item should not be scrutinised. Instructions to patients are included in the questionnaire. The respective procedure for illiterate patients (if included) is described in the [appendix 10.2](#).

5.1.3 Chronic Heart Failure Questionnaire Self Administered Standardized

The CHQ-SAS is a heart failure-specific PRO measure that assesses the patients' perception of their heart failure and measures the impact of heart failure symptoms. The CHQ-SAS refers to the CHQ-self-administered format and contains 16 standardised questions pertaining to 3 domains: dyspnea, fatigue and emotional function. Items are rated on a 7-point Likert scale ranging from 1 (e.g. extremely short of breath) to 7 (e.g. not at all short of breath) [[R17-2969](#)].

Patients will complete the first administration of the questionnaire at Visit 2 and complete the follow-up administration questionnaire at Visits 3 and 4 and early discontinuation (if applicable).

Please refer to [section 6.2.2](#) for order of completion of patient reported outcome measures.

Please refer to [appendix 10.3.2](#) for the first administration of the questionnaire and the ISF for the follow-up administration of the questionnaire.

5.1.4 NT-proBNP

Samples for NT-proBNP will be collected at Visit 1 (Screening) to determine whether the patient is eligible for the trial. Further samples for NT-proBNP will be collected at later time points in the trial (see [Flow Chart](#)) to investigate a potential effect of the trial medication. Samples for NT-proBNP will be analysed at the Central Laboratory.

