Safety criteria:	
 Adverse events (AE) Serious adverse events (SAE) AE of special interest (AESI) (hepatic injury, decreased renal function and ketoacidosis) Incidence and intensity of AE including serious AE (SAE) Withdrawal from trial medication due to AE Clinically relevant new finding or worsening of existing condition on physical examination Clinically relevant changes in laboratory measurements from baseline Heart rate and blood pressure in conjunction with exercise

	
testing
 
• ECG findings at scheduled visits reported as AEs
Statistical methods:	
The primary model will be a Wilcoxon rank test on change from baseline to week 12 in 6MWT.
 
The primary model will be conducted on all randomized patients.
 
Both key secondary endpoints will be tested using a Wilcoxon rank test, and both will be tested if the primary endpoint revealed a significant result in favour of empagliflozin. For adjustment of multiplicity of the two key secondary endpoints a Hochberg procedure will be followed.
 
The other secondary endpoints will not be part of the testing hierarchy.
 
Change from baseline to week 6 in exercise capacity as measured by the distance walked in 6 minutes will be evaluated using the same model as for the primary endpoint
 
Change from baseline to week 12 of Clinical Congestion Score will be evaluated using a mixed model repeated measure analysis over time. The model will include the factor treatment and the linear covariate of baseline Clinical Congestion Score.
 
Proportion of patients in every category of global impression of change at week 12 will be evaluated using Cochran-Mantel-Haenszel test.
 
Proportions of patients categorized by the shift in scores between baseline and week 12 in patient global impression of severity score will be evaluated using Cochran-Mantel-Haenszel test.
 
The endpoint “Change from baseline in NT-proBNP at week 12” (after log-transformation) will be evaluated using a mixed model repeated measure analysis over time with baseline log-transformed NT-proBNP as a covariate without imputation of missing values.

FLOW CHART

Trial Period	Screening*	Randomized Treatment Period				FU Period
		1	2	3	4 (EOT)	
Visit	1	2	3	4 (EOT)	Early Discontinuation on Visit ¹¹	FU Visit
Trial week	-3	1	6	12		EOT/early d/c + 7 days
Days of treatment	-21 to -4	1	43	85		
Time Window	-	-	±7	±7		+7
Informed consent	X					

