In/exclusion criteria	X	X				
Demographics	X					
Medical history/Concomitant diagnoses	X					
Vital signs ¹	X	X	X	X	X	X
Physical examination	X	X		X	X	
Height	X					
Weight	X	X		X	X	
Urine Pregnancy test ²	X	X	X	X	X	
HbA1c		X		X	X	
eGFR (CKD-EPIcr formula)	X*	X	X	X	X	X
Safety lab: blood tests	X* ³	X	X ⁴	X	X	X
Safety lab: urinalysis including ketones	X*	X	X	X	X	X
ECG exam ⁵	X			X	X	
Echocardiogram ⁶	X					
NT-proBNP	X*	X	X	X	X	
6 min walk test ⁷	X ⁸	X ⁹	X	X ⁹	X	
Concomitant therapy	X	X	X	X	X	X
Adverse events	X	X	X	X	X	X
KCCQ ¹⁰		X	X	X	X	
CHQ-SAS ¹⁰		X	X	X	X	
Clinical Congestion Score		X	X	X	X	
Patient Global Impression of Severity of Heart Failure Symptoms ¹⁰		X	X	X	X	
Patient Global Impression of Severity of Dyspnea ¹⁰		X	X	X	X	

Trial Period	Screening*	Randomized Treatment Period				FU Period
Visit	1	2	3	4 (EOT)	Early Discontinuation Visit ¹¹	FU Visit
Trial week	-3	1	6	12		EOT/early d/c + 7 days
Days of treatment	-21 to -4	1	43	85		
Time Window	-	-	±7	±7		+7
Patient Global Impression of Change in Heart Failure Symptoms ¹⁰			X	X	X	
Patient Global Impression of Change in Dyspnea ¹⁰			X	X	X	
Clinician Global Impression of Severity of CHF		X	X	X	X	
Clinician Global Impression of Change in CHF Severity			X	X	X	
NYHA Classification	X	X	X	X	X	
HCRU		X	X	X	X	
Randomization (IRT)		X				
Dispense trial medication		X	X			
Return medication / Medication compliance check			X	X	X	

* The screening procedures can be performed on different days within the time window. Specifically, it is recommended to have the NT-proBNP and safety lab measures (via central lab) measured as first step, especially in patients with no previous natriuretic peptide value available from clinical routine assessment in the past 6 months (refer to [section 6.2.1](#)).

1. Blood pressure and heart rate will be measured with the patient seated and rested for at least 5 minutes.
2. For female patients of child-bearing potential, local urine pregnancy test should be performed.
3. For the screening Visit 1, the safety laboratory is limited to liver transaminases, alkaline phosphatase, haemoglobin, serum creatinine, eGFR calculation. Patients do not have to be fasting.
4. For Visit 3, the safety laboratory is limited to liver transaminases, bilirubin and serum creatinine, eGFR calculation

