6.2.2 Treatment period(s)

Randomisation will occur at Visit 2 using IRT. The patients will return to the clinic for regularly scheduled visits 6 and 12 weeks after randomisation as specified in the [Flow Chart](#). These on-site visits will assess the occurrence of safety and efficacy endpoints, trial medication compliance, concomitant therapy or intervention.

All Visit 2 assessments must be performed before the first dose is taken at the site. The assessments at Visits 3 and 4 must be performed post-dose. Patients should be instructed to take their medication on the morning of trial Visits 3 and 4. Visits should be routinely scheduled at approximately the same time of day for each visit.

At all treatment visits (Visits 2, 3 and 4/EOT) and the early discontinuation visit, patient reported outcome measures should be completed first.

Patient reported outcome measures should be completed in the following order:

- KCCQ
- PGI – Severity – Heart Failure Symptoms
- PGI – Change – Heart Failure Symptoms
- PGI - Severity - Dyspnea
- PGI - Change – Dyspnea
- CHQ-SAS

The order of the remaining assessments should be preferably completed as follows and according to the visits specified in the [Flow Chart](#):

- Physical examination, body weight, height and vital signs
- Completion of clinician impression scales and clinical congestion score by Investigator
- ECG
- 6MWT conducted in duplicate (at visits 2 and 4 only) at least 1 hour apart. At visits 1, 3 and the early discontinuation visit, only one 6MWT will be conducted.
- Laboratory sample, urine pregnancy

Testing of the 6MWT at each clinic visit should be performed about the same time of day to minimize intraday variability. Prior to performing the 6MWT the relative contraindications to exercise should be assessed as per [appendix 10.1.3](#).

All other medications the patient is receiving should be taken as instructed by the physician.

At any time during the treatment period the HF background therapy is allowed to be

adjusted and optimised according to local and international guidelines.

If any additional therapy is considered necessary for the patient's welfare during the treatment period it may be given at the discretion of the Investigator (see also restrictions in [section 4.2.2](#)).

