6.7 BASELINE, TIME WINDOWS AND CALCULATED VISITS

For serum creatinine and values based upon this measurement such as eGFR, baseline will be defined as the mean of all available measurements from the screening visit until start of randomised trial medication. For all other endpoints, baseline will be defined as the last available measurement before start of randomised trial medication.

Since the protocol specifies that all measurements are taken at visit 2 before any intake of trial medication, all measurements at the first day of drug intake are assumed to qualify as baseline measurements. For laboratory values, clock time is recorded. If a lab measurement is done after treatment start, this will not qualify as baseline measurements, except in case of HbA1c, which is considered to be a stable measurement and qualifies for baseline on the whole day of first treatment intake.

For randomised patients without any treatment intake: For serum creatinine and values based upon this measurement such as eGFR, baseline will be defined as the mean of all available measurements from the screening visit until and including the day of randomisation. For all other endpoints, baseline will be defined as the last available measurement before or on the day of randomisation.

Medication taken at baseline is any medication with start date continued or before date of first study medication intake (randomisation for patients not treated) and end date continued or on or after date of first medication intake (randomisation for patients not treated).

Measurements taken after the first intake of randomised trial medication will be considered on-treatment values if they have been obtained up to end of the parameter specific follow-up period as defined in [Table 6.7: 1](#) below and will be assigned to the randomised study drug for efficacy and safety analyses.

Measurements taken after the end of the endpoint specific follow-up period after the last intake of study drug will be considered post-treatment values.

On-treatment (for OC-OT analysis) or all post-randomisation (for OC-AD analysis) efficacy and safety measurements will be assigned to visits based on time windows around the planned visit dates. These time windows are defined based on the planned number of days after the date of first administration of study drug.

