7.5.2 Other Secondary endpoints

Other secondary endpoints will not be part of the testing hierarchy. No correction for multiple testing of the other secondary endpoints will be made.

Change from baseline to week 6 in exercise capacity as measured by the distance walked in 6 minutes will be evaluated using the same model as for the primary endpoint. If no 6MWTD is available at week 6, an imputed value as defined in [Section 6.6](#) will be used.

All other secondary endpoints will take into account all data, regardless of whether the patient was on treatment or not, and without imputation of missing values (OC-AD).

The other continuous endpoints are generally analysed in an MMRM, including visit-by-treatment interaction and baseline-by-visit interaction. An unstructured covariance structure will be used to model the within-patient errors. The MMRM analyses will also be shown graphically.

Descriptive statistics will be calculated for the value at visit and change from baseline.

Shift from baseline score to 12 week score will be tabulated descriptively for single items collected in the context of the clinical congestion score (dyspnea, orthopnea, fatigue, jugular venous distension, rales and edema).

The endpoint “Change from baseline in NT-proBNP at week 12” (after log-transformation) will be evaluated using an MMRM analysis over time with baseline log-transformed NT-proBNP by visit interaction and visit by treatment interaction as covariates without imputation of missing values. Estimates obtained from the model will then be back-transformed and reported on the original scale. The MMRM analyses will also be shown graphically.

Proportion of patients in every category of global impression of change at week 12 will be evaluated using Cochran-Mantel-Haenszel test on the difference in mean treatment scores, using modified ridit scores.

Proportions of patients categorised by the difference in scores between baseline and week 12 in patient global impression of severity score will be evaluated using a Cochran-Mantel-Haenszel test on the difference in mean treatment scores, using modified ridit scores. Difference in score will be defined as the number of categories improved/deteriorated from baseline. Shift from baseline score to 12 week score will be tabulated descriptively.

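### The MMRM for change in log NT-proBNP adjusts for one pre-treatment value although two are measured: a missed gain in precision, not an error

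*Protocol*

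**What the plan says.** - **Two samples before treatment.** Protocol 5.1.4 on the first: "Samples for NT-proBNP will be collected at Visit 1 (Screening) to determine whether the patient is eligible for the trial". The Flow Chart row reads "NT-proBNP X* X X X X", that is Visits 1 to 4 and the early discontinuation visit. Visit 1 falls on days -21 to -4 and Visit 2 on day 1.
- **The second is pre-dose.** Protocol 6.2.2: "All Visit 2 assessments must be performed before the first dose is taken at the site".
- **One laboratory.** Protocol 5.1.4: "Samples for NT-proBNP will be analysed at the Central Laboratory".
- **Baseline.** Protocol 7.3 and SAP 6.7 agree. Outside creatinine and values derived from it: "For all other endpoints, baseline will be defined as the last available measurement before start of randomised trial medication". For creatinine and eGFR: "baseline will be defined as the mean of all available measurements from the screening visit until start of randomised trial medication".
- **Model.** SAP 7.5.2: the log-transformed change "will be evaluated using an MMRM analysis over time with baseline log-transformed NT-proBNP by visit interaction and visit by treatment interaction as covariates". There is no term for the screening value.
- **Status.** The endpoint is an other secondary endpoint, outside the testing hierarchy (Protocol 7.1, SAP 7.5.2) and evaluated in an exploratory manner (Protocol 7.2).

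**The concern.** A single natriuretic peptide value is a noisy measure of a patient's underlying level. Two values taken up to about three weeks apart, before any study drug, usually locate that level better than one. Inclusion criterion 7 rests on the Visit 1 central result, so nearly every randomised patient should have it. When Visit 2 is also available, the model leaves the Visit 1 value out. What is at stake is the width of the confidence interval for the only laboratory measure among the secondary endpoints. Bias and type I error are not at issue.

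**Working it through.** **Figures in the plan.** There is none to reproduce. Protocol 7.7 and 7.7.1 cover 6MWT, KCCQ-TSS and CHQ-SAS dyspnea only. No SD, correlation, effect size or power is given for NT-proBNP, so every input below is an assumption, shown with a range.

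**Step 1: stable level during screening.** On the log scale let s be the between-patient SD (0.7-0.9), e the short-term within-patient SD (0.2-0.4) and d the SD of drift to week 12 (0.2-0.4). With k pre-treatment values:

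- λ_k = s² / (s² + e²/k)
- residual variance R_k = s²(1 − λ_k) + d² + e²

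| s, e, d | λ₁ | λ₂ | R₁ | R₂ | R₂/R₁ |
|---|---|---|---|---|---|
| 0.7, 0.2, 0.4 | 0.49/0.53 = 0.925 | 0.49/0.51 = 0.961 | 0.2370 | 0.2192 | 0.925 |
| 0.9, 0.4, 0.2 | 0.81/0.97 = 0.835 | 0.81/0.89 = 0.910 | 0.3336 | 0.2728 | 0.818 |

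These are the extremes of the grid: 7.5% to 18% less residual variance.

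**Step 2: drift during screening as well.** Step 1 places all drift after Visit 2. Let the same drift run as a random walk over a 22-day screening gap, adding variance g = d² × 22/84 between Visits 1 and 2. For the first row g = 0.0419, and then:

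- Var(V1) = 0.53, Var(V2) = 0.5719, Cov(V1,V2) = 0.49
- Var(Y) = 0.7319, Cov(V1,Y) = 0.49, Cov(V2,Y) = 0.5319
- V2 only: 0.7319 − 0.5319²/0.5719 = 0.2372
- further reduction from V1: (0.49 − 0.49 × 0.5319/0.5719)² / (0.53 − 0.49²/0.5719) = 0.0107
- ratio: 0.2265/0.2372 = 0.955

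The second row gives 0.826. The range becomes 4.5% to 17%.

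**Step 3: correlations instead of variance components.** Write a, b and c for the correlations V1-V2, V2-week 12 and V1-week 12. The residual variance is 1 − b² with V2 alone and falls by (c − ab)²/(1 − a²) when V1 is added.

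| a / b / c | Ratio |
|---|---|
| 0.9 / 0.8 / 0.80 | 0.906 |
| 0.8 / 0.7 / 0.65 | 0.956 |
| 0.9 / 0.8 / 0.76 | 0.977 |
| 0.9 / 0.8 / 0.72 (c = ab, Markov decay) | 1.00 |

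If all three correlations equal ρ, the ratio is (1 + 2ρ)/(1 + ρ)². That is 0.889 at ρ = 0.5 and 0.776 at ρ = 0.9, the most favourable form, with no decay and no selection on Visit 1.

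**Step 4: selection at Visit 1.** The entry cut (>300 pg/ml, or >600 pg/ml with atrial fibrillation) truncates Visit 1 and shrinks the gain. In simulation with equal correlation and 10% to 50% of screened patients cut off, the ratio is 0.91-0.95 at ρ = 0.5 and 0.79-0.82 at ρ = 0.9. With both cuts applied in four assumed settings, the reduction was 4-12%.

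**Step 5: validity under selection.** Visit 1 precedes randomisation, so adjusting for it does not bias the comparison even though patients were selected on it. Simulated null rejection, with entry truncated at 300 pg/ml, was 4.6-5.4%.

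**Step 6: averaging is the weaker remedy.** With the mean of V1 and V2 as covariate the residual variance is 1 − ((b + c)/2)² / ((1 + a)/2). At 0.9/0.8/0.72 this is 1 − 0.76²/0.95 = 0.392, against 0.36 for V2 alone: a ratio of 1.09, so precision is lost. Averaging would also carry the entry cut, through regression to the mean, into the reported change in both arms.

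**The case against.** The strongest reply is that nothing is wrong. Protocol and SAP define baseline identically, the model follows that definition, Protocol 5.1.4 gives the screening and later samples separate purposes, and no confirmatory conclusion depends on this endpoint. All of that stands.

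Four stronger readings are tempting and are not supported:

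- *The plan contradicts itself because creatinine and eGFR use all pre-treatment values.* That rule averages, which step 6 shows can be the worse choice here. It is a different method for a different analyte, not an inconsistency that needs correction.
- *Visit 1 serves eligibility only.* Under SAP 6.7 the Visit 1 value becomes the baseline when Visit 2 is missing or its sample is timed after treatment start. A second covariate would then repeat the same number unless a rule is written.
- *Power would rise by a stated amount.* The documents set no effect size. Simulations with an assumed effect of -0.15 log units gave rises of 3 to 7 points (77% to 80%, 72% to 79%, 62% to 69%). They applied only the 300 pg/ml cut and say nothing firm about this trial.
- *SBP and DBP need the same change.* They too are taken at Visits 1 and 2, but no gain was calculated for them, and Protocol 10.6 adds a both-arms procedure at Visit 1. That extension is optional at most.

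It is also fair to object that the remedy needs more than one sentence. A failed NT-proBNP criterion excludes nobody from analysis (SAP Table 6.2:1, A1.08). Laboratory results may be re-tested once, and screening results may carry over from trial 1245-0168 (Protocol 3.3).

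**Conclusion.** The point holds as an inexpensive improvement. The direction is firm: in large samples a second pre-randomisation covariate cannot raise the residual variance, and it lowers it unless Visit 1 adds nothing to Visit 2. The size is not firm. Under the assumed variance components the reduction is roughly 4-18%. The standard error falls by about 2% (1 − √0.955 = 0.023) to 10% (1 − √0.818 = 0.096). Slow decay of correlation over time pushes the gain towards the low end, and Markov decay removes it. A reader should not infer that the planned NT-proBNP result would be biased or invalid, or that any hierarchical test is affected.

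**What to change.** Before unblinding, amend SAP 7.5.2 as follows:

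1. Add log NT-proBNP at Visit 1, by visit, as a second covariate. Keep the last pre-treatment value as baseline and change from it as the response. Do not average the two values.
2. State that the last valid Visit 1 (screening) result is used if the test was repeated.
3. State that a patient with only one pre-treatment value stays in the model, for example by single imputation of the missing covariate from the pooled, blinded pre-treatment data.

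This needs no new samples. It costs one or two degrees of freedom and the short handling rule in items 2 and 3. Leave SBP and DBP as planned, or treat the same change there as optional.
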